***6.12.5.7 Frequency and severity of any vertigo at day 1,7,14, 28 and 84***

For each relevant timepoint the number and percentage of patients reporting vertigo will be summarized by treatment group. Severity of reported vertigo episodes will be summarized as counts and percentages as well on a scale from 0 (no vertigo) to 10 (extreme vertigo). The frequency of patients experiencing vertigo will also be displayed graphically for each treatment group and timepoint via a bar chart.

All data on reported vertigo episodes will also be listed.

***6.12.5.8 Tinnitus burden based on the change in tinnitus QOL scores at day 1,7,14, 28 and 84***

The Tinnitus Functional Index (TFI) comprise of 25 questions on the impact of the tinnitus on the individual behavior and feelings in which items 1 and 3 are in percentage scale, that is, from 0 to 100 with increment of 10 while all the other items are in 0 to 10 scale with an increment of 1. Thus, items 1 and 3 need to be transformed into a 0 to 10 scale by dividing the value by 10 before obtaining the subscale score to which the items belong, as well as the total TFI score. The questionnaire has eight subscales that address the intrusiveness of tinnitus (items 1, 2, 3), the sense of control the patient has (items 4, 5, 6), cognitive interference (items 7, 8, 9), sleep disturbance

	Sponsor:	Sensorion
	Protocol Number:	SENS 401-201
STATISTICAL ANALYSIS PLAN. PHASE 2-3-4		

(items 10, 11, 12), auditory issues (items 13, 14, 15), relaxation issues (items 16, 17, 18), quality of life (items 19, 20, 21, 22), and emotional distress (items 23, 24, 25). In obtaining the subscale score, the response to all the items that belong to the corresponding subscale score will be added then divided by the number of items that have responses, and eventually multiplied by 10. Thus, the subscale score would range from 0 to 100. For a valid subscale score, no more than 1 item should have missing response. Otherwise, the subscale score will be set to missing. The TFI total score is obtained by adding the values of all the items that have responses then dividing by the number of items that have responses, and eventually multiplying by 100. TFI total score will range from 0 to 100. For a valid TFI total score, there should be at least 19 items that have non-missing responses. Otherwise, the TFI total score will be set to missing.

The TFI subscale scores and total score, along with the corresponding changes from baseline will be summarized for all the relevant timepoints by treatment group. All responses to TFI items, as well as derived TFI data (total and subscale scores) will be listed.

**6.12.5.9 Change in biomarkers**

Prestin results and its change from baseline will be summarized descriptively at baseline, Day 14, and Day 28 (EoT).

All biomarker data will be listed.

**6.12.5.10 Change in EQ-5D-5L scores between baseline and Day 28 and 84**

EQ-5D is a standardize measure of health status that consists of two parts: health-status descriptive system questionnaire which provides a simple descriptive profile of the responder’s health, and EQ visual analogue scale (VAS) which is a quantitative measure of the responder’s overall health based on his/her own judgement. The descriptive system comprises five dimensions (mobility, self-care, usual activities, pain/discomfort, anxiety/depression) with five response levels (no problems, slight problems, moderate problems, severe problems, unable to/extreme problems). Meanwhile, VAS ranges from 0 to 100 which corresponds to ‘worst health you can imagine’ to ‘best health you can imagine’ respectively.

The number of patients reporting each response level for each of the five dimensions will be summarized by treatment group for each baseline and post-baseline visits. Shift tables from baseline to post-baseline visits will also be presented for each dimension. In addition, a summary of dichotomize response, that is, ‘no problem’ when the response is level 1 (“no problems” or “no pain or discomfort” or “not anxious or depressed”) and ‘any problems’ when the response is level

	Sponsor:	Sensorion
	Protocol Number:	SENS 401-201
STATISTICAL ANALYSIS PLAN. PHASE 2-3-4		

2 to 5 (any other responses), will be presented by treatment group for the baseline and post-baseline visits.

The EQ Visual Analogue Scale (VAS) and its change from baseline to Day 28 (EoT) and Day 84 (EoS/Follow-up) will be summarized by treatment group.

All EQ-5D-5L data will also be listed.

**6.12.5.11 Change in DPOAE at Days 7, 14, 28, and 84 compared to baseline values**

The corresponding assessments were optional in the protocol leading to data available in only a small subset of subjects. For each collected variable, descriptive statistics by treatment group and visit will be presented for the affected ear.

**6.12.5.12 Change in TEOAE at Days 7, 14, 28 and 84 compared to baseline values**

The corresponding assessments were optional in the protocol leading to data available in only a small subset of subjects. For each collected variable, descriptive statistics by treatment group and visit will be presented for the affected ear.

**6.12.6 Multiplicity**

Multiplicity adjustment for comparing treatment groups in part 1 (3 treatment groups) for a given endpoint is addressed by testing first the high dose versus placebo and then testing the low dose versus placebo conditionally to the significance of the high dose as described in Section 6.12.2. As for the secondary endpoints, analyses will be carried out after the primary endpoint following a sequential testing procedure. The order of testing will be as follows:

1. Change in pure tone audiometry (PTA; average of the hearing threshold of 3 contiguous most affected hearing frequencies in decibels as identified at study entry) in affected ear from baseline to the end of treatment visit (Visit D28± 3) [primary endpoint]
2. Change in pure tone audiometry (average of the hearing threshold of the 2 most affected hearing frequencies identified at study entry) in affected ear from baseline to the end of treatment visit (Visit D28± 3)
3. Change in pure tone audiometry (the most affected hearing frequency identified at study entry) in affected ear from baseline to the end of treatment visit (Visit D28± 3).
4. Change in pure tone audiometry (PTA; average of the hearing threshold of 3 contiguous most affected hearing frequencies in decibels as identified at study entry on pure tone

	Sponsor:	Sensorion
	Protocol Number:	SENS 401-201
STATISTICAL ANALYSIS PLAN. PHASE 2-3-4		

audiometric air conduction testing) in affected ear from baseline to the end of study visit (Visit D84 ± 3)

5. Change in speech discrimination threshold from baseline to
  - a. Days 28,
  - b. and 84
6. Frequency and severity of tinnitus at Days 7, 14, 28, and 84 assessed by numerical rating scale
  - a. severity at Day 28
  - b. severity at Day14
  - c. severity at Day 7
  - d. severity at Day 84

Thus, if significance is not achieved on the higher-ranking endpoint, analysis of lower-ranking endpoints will still be conducted but will be purely exploratory. For example, if significance is not achieved in 2, analysis of 3-6 will still be conducted but will be declared as non-significant and thus purely exploratory. For the Part 1, the high dose will be tested, first, within each secondary endpoint (i.e. 2, 3, 4, 5), then followed by testing the low dose conditionally to the significance of the high dose.

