#### **13.5.2 Analysis of secondary efficacy endpoints**

Mean changes from baseline in pure tone audiometry (average of the hearing threshold of the 2 most affected hearing frequencies identified at baseline) in affected ear will be analysed using the same modeling approach as for the primary endpoint, but reporting estimates with unadjusted p-values.

Mean changes from baseline in pure tone audiometry (the most affected hearing frequencies identified at baseline) in affected ear will be analysed using the same modeling approach as for the primary endpoint, but reporting estimates with unadjusted p-values.

Mean changes from baseline of the speech recognition threshold at Days 7, 14, 28 and 84 will be analysed using the same modeling approach as for the primary endpoint, but reporting estimates with unadjusted p-values.

Mean changes from baseline of the severity of tinnitus (assessed numerical rating scale) at Days 7, 14, 28 and 84 will be analysed using the same modelling approach as for the primary endpoint, but reporting estimates with unadjusted p-values.

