#### 4 SAMPLE SIZE

The sample size is based on the primary endpoint: average change in PTA in dB between the baseline and week 4 (Day 28±3d) on the 3 most affected contiguous frequencies.

**Part 1:** A sample size of 111 patients (37 patients per treatment arm) was retained corresponding to following assumptions:

- Each comparison to placebo performed at 5% one-sided significance level (with higher dose to be tested first and low dose to be tested conditionally to the high dose significance)
- Power of each comparison to placebo set to 75%.
- Randomization ratio 1:1:1
- Intra-group standard deviation of 30 dB is estimated based on recent publication in SSNHL with other pharmaceutical therapies and blinded examination of variance (with a 0.45 correlation between Day 28 and baseline)
- A difference to placebo of 15 dB is expected, which would be considered clinically meaningful
- The corresponding fixed design sample size of 105 patients (35 patients per treatment arm) was then inflated to 111 patients (37 patients per treatment arm) to allow the use of a group sequential test (GST) design with 3 looks (2 interim looks and a final look).

This design of Part 1 was introduced in the protocol amendment leading to version 4.0. The revised assumption of the intra-group standard deviation (adjusted for baseline) of 30 dB was based on a blinded review of the variability of 63 patients, which led to an estimate of the adjusted standard deviation more in line with the 27 dB seen in a recent publication in SSNHL1 than with the 20dB seen in the publication used at time of the protocol initiation2. The choice of the power level and of the significance level, combined with the strategy of testing the low dose conditionally after the high dose, was guided by the unexpected low recruitment rate observed in the study. The 3-look GST design (interim looks plus one final part 1 analysis) was introduced in order to allow an early discontinuation (for futility or for efficacy) of Part 1.

	Sponsor:	Sensorion
	Protocol Number:	SENS 401-201
STATISTICAL ANALYSIS PLAN. PHASE 2-3-4		

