### **Analysis of Part 1**

To preserve type I error rate during part 1, the above hypotheses will be tested according to a fixed-sequence testing strategy: the comparison of the high dose versus placebo will be tested first at 5% one-sided significance level; then the comparison of the low dose versus placebo will be tested at 5% one-sided significance level conditionally to the significance of the high dose. This procedure is compliant with the principle of the closed test procedure (Marcus et al., 1976, Koch 1996). In the event that the null hypothesis  $H_{0H}$  cannot be rejected for the high dose, the p-value associated with  $H_{0L}$  will still be provided but considered exploratory. The comparison of the high dose versus the low dose will be considered exploratory.

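### SAP 6.12.6 does not say which dose must succeed before the next Part 1 endpoint opens; on its natural reading the error over primary plus secondary endpoints exceeds 5% one-sided

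*SAP*

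**What the plan says.** For the primary endpoint in Part 1 the rule is clear. SAP 6.12.2 (Analysis of Part 1) states: "To preserve type I error rate during part 1, the above hypotheses will be tested according to a fixed-sequence testing strategy". The high dose is compared with placebo first, then the low dose if the high dose is significant, each at 5% one-sided.

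For the secondary endpoints, SAP 6.12.6 gives two rules.

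- Between endpoints: "if significance is not achieved on the higher-ranking endpoint, analysis of lower-ranking endpoints will still be conducted but will be purely exploratory". Neither this sentence nor the example after it (failure on endpoint 2 makes 3 to 6 exploratory) names a dose.
- Between doses, Part 1 only: "the high dose will be tested, first, within each secondary endpoint (i.e. 2, 3, 4, 5", with the list closing there, "then followed by testing the low dose conditionally to the significance of the high dose". Endpoint 6 is not in that list, although 6a to 6d are in the testing order.

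The section opens by describing the dose adjustment as applying to a given endpoint. Protocol 13.5.2 had planned only "reporting estimates with unadjusted p-values" for the secondaries. SAP Section 8, item 5, records that multiplicity adjustment was then specified for both parts.

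**The concern.** A fixed sequence holds its error rate because only one test is open at a time and any failure closes the rest. If the high dose alone opens each endpoint, a significant high-dose result opens two tests at full 5%: the low dose on the same endpoint and the high dose on the next one. Neither depends on the other. An ineffective low dose then gets a fresh 5% test at every endpoint the high dose reaches, whether or not it failed before.

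What is at stake is the label on low-dose secondary results in the Part 1 report. A low dose that missed on Day 28 PTA could be reported as significant on Day 84 PTA or speech threshold, as though within a 5% family. Two statisticians following 6.12.6 in good faith could also label the same result differently.

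**Working it through.** **Inputs from the documents.** One-sided 5% for each comparison with placebo; 1:1:1 allocation, so the two dose-versus-placebo statistics on an endpoint correlate 0.5 through the shared placebo arm; 37 per arm; difference 15 dB; SD 30 dB with a 0.45 baseline correlation (SAP Section 4). Testing order 1, 2, 3, 4, 5a, 5b, 6a, 6b, 6c, 6d (SAP 6.12.6): ten steps, or six if endpoint 6 is left out, as the last sentence's list does.

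**Assumptions not in the documents.** Exchangeable correlation between endpoints, range 0.5 to 0.9. Low dose null on every endpoint. High dose either certain to pass everywhere, or at the planned effect on every endpoint.

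**The plan's own figures.**

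- Adjusted SD = 30 × √(1 − 0.45²) = 26.79.
- n per arm = 2 × (26.79/15)² × (1.645 + 0.674)² = 34.3, so 35 per arm and 105 in total, as stated.
- At 37 per arm the expected z is 15 / (26.79 × √(2/37)) = 2.41, and power is Φ(2.41 − 1.645) = 77.7%. This is the planned high-dose effect used below.
- Primary pair, high then low: with the high dose certain to pass and the low dose null, error is 5.0%. That is its maximum, so the 5% claim reproduces.

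**Natural reading.** The low-dose test on step k counts if the high dose passed steps 1 to k and the low dose passes step k. With independent endpoints and a certain high dose, the chance of a false low-dose claim is 1 − 0.95⁶ = 26.5% over six steps and 1 − 0.95¹⁰ = 40.1% over ten. Correlation lowers this. Simulation (one million runs, critical z 1.645):

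| Steps | Endpoint correlation | High dose certain | High dose at planned effect | Of the planned-effect column: low dose failed the primary, then gained a secondary |
|---|---|---|---|---|
| 6 | 0.5 | 18.6% | 15.2% | 10.2% |
| 6 | 0.7 | 14.8% | 13.0% | 8.1% |
| 6 | 0.9 | 10.0% | 9.5% | 4.6% |
| 10 | 0.5 | 24.7% | 18.2% | 13.4% |
| 10 | 0.7 | 18.5% | 15.6% | 10.7% |
| 10 | 0.9 | 11.6% | 10.8% | 5.9% |

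At correlation 0.95 and the planned effect the totals are still 8.0% (six steps) and 8.9% (ten).

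**Other readings and states.**

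- Both doses must pass an endpoint before the next opens: 5.0% at most.
- The low dose must also have passed its own earlier endpoints, but the high dose moves on regardless: up to 9.7%, when the high dose works on the primary only. The low dose on endpoint 1 and the high dose on endpoint 2 are then both open at 5%.
- No dose works on anything: 5.0% under every reading. The excess needs a high dose that works.

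**The case against.** The strongest reply is that the between-endpoint rule is not limited to the high dose. Read as covering both doses, it makes everything after a low-dose failure exploratory, and the error is 5%. This stands as a possible reading. A reader might infer that conditioning on the high dose is the only condition in the SAP, or that the SAP is shown to exceed 5%. The text supports neither; it is ambiguous by dose. But the strict reading has a large consequence that the SAP never states: a null low dose fails the primary with probability at least 95%, and each such failure would end confirmatory testing of every high-dose secondary.

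Four further limits stand.

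- The statement "This procedure is compliant with the principle of the closed test procedure" concerns the two primary hypotheses, where it is correct. It should not be read as a false claim about the secondaries.
- A reader might infer that a spurious secondary result feeds dose selection. Protocol 7.2 bases selection on benefit/risk with Day 28 PTA for efficacy, and Protocol 7.3 and 12.8.1 supply the committee with primary-endpoint efficacy data once patients have completed the 4-week treatment. Nothing shown makes a secondary p-value an input, and full Day 84 data would not exist at that point.
- 25% is not an expected figure. It needs ten steps, correlation 0.5 and a certain high dose. Endpoints 2 and 3 use frequencies drawn from the primary's three, in the same ear at the same visit, so their correlation with it may be well above 0.5.
- Part 2 has one active arm and its own patients, so the dose ambiguity does not arise there.

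**Conclusion.** The point holds as a gap in specification with a material effect. SAP 6.12.6 does not define endpoint success by dose, and its dose rule, framed endpoint by endpoint, most naturally lets the low dose be tested wherever the high dose has passed. On that reading the 5% one-sided level is not held over primary plus secondary endpoints in Part 1 when the high dose works and the low dose does not. The excess was present at every correlation tried. Its size depends on the assumed correlations and on whether endpoint 6 is included. The primary comparisons are unaffected.

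It should be corrected because the SAP chose to add multiplicity control to a protocol that had planned none for the secondaries, and the added procedure has to deliver it.

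**What to change.** Replace the last sentence of SAP 6.12.6 with one explicit serial list of all dose-by-endpoint tests for Part 1, including 5a to 5b and 6a to 6d. State that the first non-significant test ends confirmatory claims and that all later tests are exploratory. Either of these orders held the error at 5% in every configuration tried:

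- Alternating: high dose endpoint 1, low dose endpoint 1, high dose endpoint 2, low dose endpoint 2, and so on to 6d. This keeps the primary sequence of SAP 6.12.2. Its cost is that a low-dose failure ends confirmatory testing of all later high-dose secondaries.
- All high-dose steps, then all low-dose steps. This protects the high-dose secondaries. Its cost is that any high-dose secondary failure blocks the low-dose primary claim, so SAP 6.12.2 and the low-dose rule in Protocol 13.5.1 (Final analysis of Part 1) would have to change with it.

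The choice is the sponsor's. Only adding that the low dose must have passed its own earlier endpoints is not enough, as the 9.7% shows. Apart from the trade-off in the order chosen, the cost is SAP wording; no extra patients or data are needed.

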### 6.13 Pharmacokinetic Analyses

Serum samples will be collected for pharmacokinetic (PK) analysis at pre- and post-dose on Day 14 (V4) and on Day 28 (EoT). Plasma concentration values will be summarized at each relevant timepoint by treatment group using number of non-missing observations, geometric mean, geometric coefficient of variation (CV), defined as  $100 * \sqrt{(e^{s^2} - 1)}$  where  $s$  is the SD of the data on a log scale, minimum and maximum.

All PK data will also be listed.

### 6.14 Safety Analyses

The safety analyses will be presented by the treatment actually received for the Safety analysis set. In the situation of accidental dispensation of two or three distinct treatments to the same patient, the patient will be counted for the whole study on the highest dose received.

#### 6.14.1 Adverse Events

	Sponsor:	Sensorion
	Protocol Number:	SENS 401-201
STATISTICAL ANALYSIS PLAN. PHASE 2-3-4		

A treatment emergent adverse event (TEAE) is defined as any AE that has an onset on or after the first dose of study drug (without limitation after end of treatment).

Events with treatment status unclear because the onset date and/or the dates of first/last study drug intake are missing or incomplete will be considered as TEAEs.

Late AE is defined as any AE that has an onset on or later than 3 days after the last study treatment intake.

A treatment-related AE is defined as an AE as being possibly or probably related to the study drug. If an AE has missing or not assessable relationship it is assumed to be related to the study drug for analysis purposes.

Maximum severity will be assumed for an AE with missing severity.

All AEs will be coded using the most recent MedDRA version available at time of database lock. Summaries over system organ class (SOC) and preferred term (PT) by treatment groups, and listings of all TEAEs, Serious Adverse Events (SAEs), AEs leading to withdrawal, and AEs leading to death will be presented. The following tables will be presented for AEs:

- Overall incidence and the number of TEAEs, treatment-related TEAEs, SAEs, TEAEs leading to withdrawal, and TEAEs leading to death.
- TEAE by system organ class and preferred term, incidence and number of events
- Treatment-related TEAE by system organ class and preferred term, incidence and number of events
- Serious TEAE by system organ class and preferred term, incidence and number of events
- Severe TEAE by system organ class and preferred term, incidence and number of events
- TEAE by system organ class, preferred term and maximum severity, incidence
- Treatment-related TEAE by system organ class, preferred term and maximum severity, incidence
- TEAE leading to early withdrawal by system organ class and preferred term, incidence and number of events
- Listing of serious AEs (presented in the Table section of the appendices).
- Listing of AEs leading to withdrawal (presented in the Table section of the appendices)
- Listing of AEs leading to deaths (presented in the Table section of the appendices).

	Sponsor:	Sensorion
	Protocol Number:	SENS 401-201
STATISTICAL ANALYSIS PLAN. PHASE 2-3-4		

In counting the number of AEs reported, a continuous event (i.e. reported more than once and which did not cease), will be counted only once; non-continuous AE reported several times by the same subject will be counted as multiple events.

A late TEAE is defined as a TEAE that has an onset date 3 days or more after the last intake of study drug.

The outputs listed above will be repeated on the late TEAEs only.

All AEs will be listed (with flags identifying TEAEs and late TEAEs).

SAEs not classified as treatment-emergent will be displayed in a separate listing.

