### 12.4 Reporting of adverse events

#### 12.4.1 Adverse events

Any AE occurring after the patient has signed the informed consent must be fully recorded on the patient's e-CRF. The AE form should be supported by a complete documentation available in the patient's file.

Any abnormal laboratory test or ECG considered medically meaningful (e.g., causing the patient to withdraw from the study, requiring treatment or causing apparent clinical manifestations, or judged medically relevant by the investigator) should be reported as an AE. The test should be repeated as soon as possible for confirmation. The AE should be fully described along with start and stop dates, severity, relations to the investigational product, action taken and outcome in the AE form.

For any adverse event, the investigator has to follow-up the case to determine the outcome of the adverse event. He should also try to get all necessary information to assess whether the AE meets the criterion definition of a non-serious or a serious adverse event (SAE). In the later case, it will trigger immediate notification to the Sponsor (see below). Whichever the seriousness criterion, follow-up of the AE is requested until final outcome in case of ongoing adverse event or ongoing complication even after the treatment is discontinued.

Final outcome includes complete resolution or stabilization at a level acceptable to the investigator and the Sponsor. For subjects withdrawn from the study treatment and subjects experiencing AE at the end of the study and within 30 days following the last treatment day, the investigator will manage the appropriate follow up (if required until the AEs are resolved or attributed to a cause other than the study drug).

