#### **13.5.4.1 Adverse events**

Each adverse event will be coded to a “Preferred Term” and associated “System-Organ Class” according to an established and validated adverse reaction dictionary (MedDRA) before the randomised treatment code is broken. The adverse event endpoints are number of subjects experiencing:

- at least one event,
- an event under each recorded Preferred Term,
- an event under each recorded System-Organ Class.

These endpoints apply to all adverse events, regardless of relationship of the event to the study drug.

All safety analyses will be performed on the safety analysis set using descriptive statistics.

Adverse events (AEs) will be evaluated for severity and coded using MedDRA. They will be summarized by system organ class and preferred term. Separate summaries of treatment-emergent AEs (TEAEs) will be generated for the following:

- All TEAEs
- Severe TEAEs
- Serious TEAEs
- TEAEs leading to treatment discontinuation
- TEAEs resulting in death

Treatment-emergent adverse events (TEAE) are defined as events occurring after the first dose intake of randomised study drug, and up to and including five half-lives after the last dose of study drug. Additionally, events present before the first dose of randomised study drug, but worsening under treatment are considered as TEAE. Events with treatment status unclear because the onset date and/or the dates of first/last study drug intake are missing or incomplete will be considered as TEAEs.

An AE that will not qualify as a TEAE will be considered as a Non-TEAE.

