9. Definition of treatment-emergent adverse events was modified to have no limitation in time after the last dose intake of study drug (instead of excluding events occurring later than five half-lives after the last lost dose). Late TEAEs were defined as TEAEs with onset date on 3 days or more after the last study drug intake.
10. Number and percentage of subjects with treatment-emergent abnormality was added in the analysis of laboratory data and vital signs.

	Sponsor:	Sensorion
	Protocol Number:	SENS 401-201
STATISTICAL ANALYSIS PLAN. PHASE 2-3-4		

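### SAP 6.14.1 drops the protocol's rule that pre-dose events worsening on drug are treatment-emergent, and SAP section 8 does not declare the change

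*SAP*

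**What the plan says.** Protocol 13.5.4.1 builds the TEAE definition from three parts. The first covers "events occurring after the first dose intake of randomised study drug", up to five half-lives after the last dose. The second reads: "Additionally, events present before the first dose of randomised study drug, but worsening under treatment are considered as TEAE". The third classes events whose status cannot be settled, because dates are missing or incomplete, as TEAEs.

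SAP 6.14.1 defines a TEAE as "any AE that has an onset on or after the first dose of study drug", with no upper limit after treatment ends. It keeps the third part: "Events with treatment status unclear because the onset date and/or the dates of first/last study drug intake are missing or incomplete will be considered as" treatment-emergent. The second part is absent.

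SAP section 8, item 9 describes how the definition departs from the protocol: "Definition of treatment-emergent adverse events was modified to have no limitation in time after the last dose intake of study drug". It then adds the late-TEAE category. It says nothing about worsening.

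On collection, Protocol 12.4.1 states: "Any AE occurring after the patient has signed the informed consent must be fully recorded". AE records can therefore carry an onset earlier than the first dose.

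**The concern.** The two definitions disagree on a class of events that safety tables are normally expected to show: something mild before dosing that becomes worse on drug. The SAP governs the clinical study report, so its narrower rule would apply.

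The change is also hidden. Item 9 of section 8 sets out to explain how the definition changed, and the one change it reports widens capture. A reader would conclude that the SAP counts everything the protocol counts, and more. It does not.

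The omission looks unintended, because the neighbouring rules in 6.14.1 are conservative: a missing relationship is treated as related, and a missing severity as maximal.

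Confirming safety is a stated secondary objective in both documents. The TEAE tables are where adverse events are compared between arms.

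**Working it through.** No arithmetic underlies the definition, so the check is clause by clause.

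| Part of the definition | Protocol 13.5.4.1 | SAP 6.14.1 | Declared in SAP section 8? |
|---|---|---|---|
| Start after first dosing | Yes, up to five half-lives after last dose | Yes, no upper limit | Yes, item 9 |
| Pre-dose event that worsens on treatment | Counted | Not mentioned | No |
| Status unclear because of missing or incomplete dates | Counted | Counted | No change to declare |

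**Is the clause restored elsewhere in the SAP?** No. The date rules in 6.2.5 move a missing start date to the first-dose date when the event is ongoing or stops at or after first dosing. They do the same for a start date with only the day missing, if it falls in the month of first dosing. These rules rescue events with uncertain dates. They do not touch an event with a complete pre-dose start date.

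**Trace one event.** Take an AE that starts after consent and before first dose, with complete dates, mild at first and severe on drug.
- Protocol: it is a TEAE through the second part.
- SAP, single record with the original start date: the start precedes first dosing and the dates are complete, so it is not a TEAE.
- SAP, worsening entered as a new record with its own start date: the new record is a TEAE.

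Neither document says which way worsening is to be recorded. The rule in 6.14.1 that a continuing event reported more than once counts only once suggests a single event, but does not settle the matter.

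**Which outputs change in the single-record case.** By the list in 6.14.1, the event is missing from the overall TEAE count and from these tables:
- system organ class and preferred term
- treatment-related
- serious
- severe
- maximum severity
- leading to withdrawal

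The late-TEAE repeats draw on the same set and also use the onset date, so a worsened pre-dose event could never be late.

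**Which outputs do not change.** All AEs are listed. The listings of serious AEs, of AEs leading to withdrawal and of AEs leading to death are not limited to TEAEs. SAEs that are not treatment-emergent have a listing of their own. In the overall summary, 6.14.1 names SAEs without restricting them to TEAEs, so a serious case stays in that count.

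**How many events.** The event must start after consent, before first dose, persist, and then worsen. Screening runs from Day -4 to Day 1, and hearing loss must have begun within 96 hours of first intake (96 / 24 = 4 days). The window is therefore about four days at most. Protocol 10.4 allows for screening and inclusion within 24 hours of each other. The documents give no rate from which a count could be derived.

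**What one event would do.** Assuming every randomised patient is treated, one reclassified patient moves an arm's incidence by 1/37 = 2.7 percentage points in Part 1 and 1/95 = 1.1 points in Part 2. With none affected, the shift is zero.

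**The case against.** The strongest reply is that little or nothing is lost in practice. The pre-dose window is short, sites may enter worsening as a new AE, and serious, withdrawal and fatal cases can still be found in the listings. Laboratory values and vital signs are also compared with baseline independently of the TEAE definition.

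Most of this stands. It limits the size of the problem and means that such events are not lost from the report. It does not remove the mismatch. Listings give no incidence by arm, and the TEAE flag in the AE listing would follow the SAP definition and so be at odds with the protocol. If new records are what the sponsor intends, the SAP needs to say so.

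Three stronger readings are tempting, and the documents do not support them.
- A reader might infer that dose selection for Part 2 is affected. SAP section 1 places the safety and efficacy analyses for the Data Monitoring Committee in a separate SAP that is not available here. Protocol 12.8.1 describes the committee's material as totals of AEs and SAEs by group, not TEAEs.
- A reader might infer that worsening is certain to vanish from every TEAE table. That depends on how worsening is recorded, which is not stated.
- A reader might assume a rate of a few per cent and derive a number of missed patients per arm. Nothing in the documents anchors such a rate, and zero is plausible.

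**Conclusion.** The SAP definition is wrong as written. It is narrower than the protocol's, no other part of the SAP makes up the difference, and section 8 does not declare it. An event with a known pre-dose start that worsens on drug would be misclassified, provided the worsening is not entered as a new record.

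The reach is the TEAE incidence tables of the clinical study reports for both parts. The number of patients affected cannot be derived and may be small or zero. The case for acting rests on the undeclared conflict between the two documents and on how easily it can be removed, not on an expected count.

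**What to change.** In SAP 6.14.1, add the protocol's own clause after the onset rule: "events present before the first dose of randomised study drug, but worsening under treatment are considered as TEAE". Keep to that wording. Extending it to changes in seriousness, or to worsening after treatment has ended, would go beyond the protocol and would need its own entry in section 8.

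In the same section, state:
- how worsening is identified: by a new AE record, or by an increase in recorded severity on the existing record
- which date the worsening takes, so that the late-TEAE rule can be applied
- how the worsened event is counted under the single-count rule for continuing events

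If the sponsor did mean to drop the clause, item 9 of section 8 should say so and give the reason.

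The cost is one extra derivation and a few lines of text. If worsening is to be read from a severity change, the sponsor should first confirm that the AE data hold a date for that change. Protocol 12.4.1 asks for start and stop dates and severity, but names no date of worsening.
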